Eplerenone for Central Serous Chorioretinopathy: A Pilot Study

Protocol

IRB#: 10722

Principal Investigator: [name]

Co-investigators: [name], [name], [name], [name], [name], [name], [name], [name]

Coordinators: [name], [name], [name]

Part I

Aim and Hypotheses:

We would like to examine the short-term effects and safety of a systemic anti-aldosterone medication, eplerenone, in a small group of patients with central serous chorioretinopathy (CSCR), an idiopathic eye disease which affects the central vision and is known to be worsened or potentiated by elevated systemic corticosteroid levels.

In rat eyes, mineralocorticoid challenges have been shown to cause similar changes in the retina and choroid (choroidal vessel vasodilation, focal leakage, and increased choroidal thickness) as found in human patients with CSCR, suggesting that mineralocorticoids may play a role in potentiating CSCR.[1] Eplerenone, a mineralocorticoid receptor antagonist, has been shown to be of visual and anatomic benefit in a small retrospective series of 4 patients with chronic CSCR, suggesting that decreasing mineralocorticoid action in the eye may improve signs and symptoms of CSCR.[1] This data is enticing, and is the only current published evidence that eplerenone may be used to treat CSCR. However, in their study, the investigators only evaluated patients with chronic CSCR, and did so in a retrospective and uncontrolled fashion in only 4 patients.[1]

Our aim is to evaluate a standardized dose of eplerenone in a controlled prospective fashion for both acute and chronic CSCR. We hypothesize that aldosterone inhibition with eplerenone will decrease choroidal vessel vasodilation, focal leakage, and choroidal thickness in patients with both acute and chronic CSCR, leading to resolution of subretinal fluid and ultimately an improvement in symptoms. Sub-retinal fluid can be precisely measured using optical coherence tomography (OCT), an imaging technique discussed below.

Background:

Epidemiology of CSCR

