Of note, even after fluid resorption, visual changes may still be reported by patients for several months after the initial episode.[15] The definition of chronic CSCR has not been agreed upon, but most of the literature defines it as sub-retinal fluid lasting more than 3 months, or recurrence of the disease within 1 year.[8-12] Chronic CSCR is also more likely to be bilateral, while acute CSCR more typically affects one eye at a time. Approximately 30-50% of all CSCR patients have recurrences of the disease, either in the same eye, opposite eye, or both eyes.[8,12] Patients with chronic CSCR can also develop intra-retinal fluid in addition to sub-retinal fluid.

Pathophysiology of CSCR

The pathophysiology of CSCR remains unclear, but recent studies using specialized imaging techniques have been helpful. CSCR is thought to be caused by an underlying abnormality in vascular permeability in the choroidal vessels, leading to elevation of the retinal pigment epithelium (RPE) from Bruch's membrane. The separated RPE may then undergo tiny rips, leading to direct connection between the choroid and the subretinal space. The RPE pump, which usually prevents accumulation of fluid under the retina, then dysfunctions or is overwhelmed, leading to build-up of serous fluid under the retina, the typical and characteristic feature of CSCR.[8,12] The abnormality in choroidal circulation is often bilateral. A familial predisposition is occasionally observed, although no clearly-defined pattern of inheritance has been elucidated.

Imaging in CSCR

Specialized imaging techniques are typically used to diagnose and follow patients with CSCR. Fluorescein angiography (FA) is the gold standard to diagnose the disease. The most characteristic finding is an expanding point of fluorescein leakage under the neurosensory detachment of the macula, seen in approximately 90% of patients.[8] Multiple points of leakage can be seen in some patients, particularly in chronic CSCR.[16] FA can be used to direct focal laser photocoagulation treatment or photodynamic therapy (both discussed below).

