- Eligible patients will be those who present with CSCR, both acute and chronic types
- 20 patients will be enrolled; participation is voluntary and all interested patients must provide written informed consent to take part in the study

- Chronic CSCR will be defined as persistent subretinal fluid on OCT ≥ 3 months after initial presentation to the eye clinic, and $< 50\%$ reduction in fluid thickness on OCT after 3 months.
- Only one eye of a participant will be included in the study, although both eyes will be evaluated. In patients with bilateral CSCR, the worse eye will be the study eye.
- Patients will be evaluated and treated at the New England Eye Center (NEEC)
- All participants will receive a standard ophthalmic examination as well as color fundus photographs, fluorescein angiography, and macular OCT (see below for specific imaging protocol).
- Treatment will be the standard dose of eplerenone, 50 mg pills taken one pill daily over four weeks
- Subjects participation will include 4 visits to the NEEC:
 - o Treatment initiation
 - o 1 week after initiation
 - o 2 weeks after initiation
 - o 4 weeks after initiation
- Prior to initiating treatment, all subjects will have laboratory testing to confirm healthy ranges of the following lab tests will include: serum potassium, creatinine, electrolytes, liver function tests, uric acid, and fasting cholesterol.
- Serum potassium and creatinine levels will be re-tested at the 1 week visit.
- All lab tests will be repeated at the 4 week visit
- Blood pressure will be measured at each visit
- A database of enrolled participants will be maintained on a password protected desktop computer at the New England Eye Center.
- When the study is complete, all data will be de-identified and coded.

Study Assessments/Schematic

Study Protocol

-4 to 5 weeks total
 -20 patients with CSCR (Acute or Chronic)

Initial Diagnosis and Enrollment

1. In order to diagnose CSCR, patients typically undergo a routine ophthalmic examination, fundus photographs, fluorescein angiography, and OCT images. Patients may undergo fundus autofluorescence testing or indocyanine green angiography at the discretion of the physician to confirm the diagnosis of CSCR. These tests are done routinely in the eye clinic and are not included as part of the study protocol.

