Both male and female participants of any race will be enrolled.

Inclusion Criteria:

1. Age 18 or over
2. Ability to give written informed consent
3. Presence of sub-retinal fluid under the fovea as seen on OCT
4. Diagnosis of Acute or Chronic CSCR:
 - a. Acute CSCR: First presentation to eye clinic with visual symptoms, including decreased vision or visual distortion, and the characteristic appearance of CSCR on examination, fluorescein angiography, and OCT.
 - b. Chronic CSCR: Previous diagnosis of CSCR, persistent subretinal fluid on OCT \geq 3 months after initial presentation to the eye clinic, and <50%

reduction in fluid thickness on OCT after 3 months. *Patients who have had previous treatment for CSCR may be included.*

Exclusion Criteria:

1. Age less than 18
2. Persons with impaired decision-making ability.
3. Women who are known to be pregnant or are actively trying to conceive.
4. Additional eye disease affecting the macula or posterior retina.
5. At screening, serum potassium concentration ≥ 5.0 mEq/L, a serum creatinine concentration >2 mg/dL in men and >1.8 mg/dL in women, or a creatinine clearance <50 mL/min, and during concomitant administration of potassium supplements, potassium-sparing diuretics, and/or potent CYP3A4 inhibitors (amifostine, cyclosporine, fluconazole, itraconazole, ketoconazole, mifepristone, posaconazole, potassium salts, Rituximab, tacrolimus, voriconazole, nefazodone, troleandomycin, clarithromycin, ritonavir, or nelfinavir).
6. Patients with type 2 diabetes will be screened for microalbuminuria with a urinalysis. If microalbuminuria is present, these patients will be excluded.

Data Elements

The data elements to be collected from each participant include age, gender, visual acuity, intraocular pressure, lens status, and retinal examination findings, color fundus photographs, fluorescein angiography images, and OCT images.

Primary Outcome

Presence or absence of subretinal fluid and/or intraretinal fluid on OCT after 4 weeks of treatment with 50 mg of eplerenone.

Secondary (Exploratory) Outcomes

- Change in central macular circle thickness on OCT, automatically calculated with OCT software after 1, 2, and 4 weeks of treatment
- Change in thickness of subretinal fluid under the fovea on OCT, manually calculated after 1, 2, and 4 weeks of treatment
- Change in thickness of choroid under the fovea on enhanced-depth imaging OCT, manually calculated, after 1, 2, and 4 weeks of treatment

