- Change in best-corrected visual acuity before and after 4 weeks of treatment
- Change in dye leakage characteristics on fluorescein angiography before and after 4 weeks of treatment
- Change in the same OCT characteristics listed above, in the fellow eye
- Proportion of acute vs. chronic CSCR patients
- Safety and tolerability characteristics in this patient population via clinical laboratory data, blood pressure, and adverse events

Data Safety and Monitoring Plan

See below for details regarding monitoring of adverse events (AEs) and serious adverse events (SAEs). Data will be monitored with the patients' safety in mind. All adverse effects will be recorded by the Principal Investigator and Co-Investigators and will be reported to the IRB at the conclusion of the study. Should an SAE occur, it will be reported immediately to the Tufts MC / TUHS IRB by the Principal Investigator within 24 hours. The Principal Investigator and Co-Investigators will be responsible for collecting the patient data information. The information will then be de-identified and coded. The key to the code will only be accessed by the investigators.

Dose adjustment and/or stopping criteria

Serum potassium criteria

If serum potassium is ≥ 5.0 mEq/L and < 5.5 mEq/L at 1 week after initiation, dosing will be decreased to 25 mg every day and serum potassium will be rechecked at 1 week. If serum potassium is still ≥ 5.0 mEq/L and < 5.5 mEq/L after 1 additional week, dosing will be decreased to 25 mg every other day and serum potassium will be rechecked at 1 week. If serum potassium is still ≥ 5.0 mEq/L and < 5.5 mEq/L after 1 additional week, dosing will be withheld. If serum potassium is ≥ 5.5 mEq/L at 1 week, eplerenone will be withheld.

See below for definition of adverse events and serious adverse events.

Statistical Analysis

The primary outcome will be described by the proportion of patients without subretinal fluid on OCT at the end of the study period (see below for sample size and precision estimates). The 95% confidence interval (CI) for this proportion will also be estimated. Descriptive statistics are considered appropriate for this pilot study since there is currently no standard treatment for CSCR, and the data from this study may be used to design future, rigorous trials of eplerenone.

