Changes in continuous secondary outcome measures will be described using mean, median, min/max, and standard deviations, and categorical secondary outcome measures will be described using frequencies and proportions.

Sample Size and Precision Calculations

The natural history of acute CSCR is to improve on its own. Studies have shown, however, that fluid resolution typically takes at least 6 weeks, and often takes as long as 3 months or longer. In a randomized study by Chan et al examining effects of half-dose photodynamic therapy in patients with acute CSCR, 20% of patients had complete resolution of fluid on OCT after 4 weeks, compared to 80% of patients treated with PDT.[12] Similar rates of complete fluid resolution have been reported after treatment with PDT, as well as in a small sample of patients with chronic CSCR treated with eplerenone.[1, 22-26] Based on these assumptions, a calculation was performed to determine the width of confidence intervals for the proportion of patients successfully

treated with eplerenone. If the treatment is effective for 70% of patients, a sample size of 10 patients will give a 95% confidence interval width of 0.586 that includes a lower bound of 0.348 (see range of widths with sample sizes of 10 and 15 below). The Research Design Center of the Clinical and Translational Sciences Institute at Tufts Medical Center assisted with these calculations.

Numeric Results for Two-Sided Confidence Intervals for One Proportion Confidence Interval Formula: Exact

Confidence Level	Sample Size (N)	Target Width	Actual Width	Proportion (P)	Lower Limit	Upper Limit	Width if P = 0.5
0.950	10		0.586	0.700	0.348	0.933	0.626
0.950	10		0.531	0.800	0.444	0.975	0.626
0.950	10		0.442	0.900	0.555	0.997	0.626
0.950	15		0.487	0.700	0.416	0.903	0.522
0.950	15		0.438	0.800	0.519	0.957	0.522
0.950	15		0.356	0.900	0.637	0.993	0.522

References

Flleiss, J. L., Levin, B., Paik, M.C. 2003. Statistical Methods for Rates and Proportions. Third Edition. John Wiley & Sons. New York.
 Newcombe, R. G. 1998. 'Two-Sided Confidence Intervals for the Single Proportion: Comparison of Seven Methods.' *Statistics in Medicine*, 17, pp. 857-872.

Safety Analysis

Safety data will be presented in tabular format and will be summarized descriptively.

PART III

1. How will participants be recruited?
 Participants will be recruited from the practices of the primary investigator and co-investigators.
2. Number of participants needed?

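### The aim covers acute and chronic CSCR, but the only outcome on type is ambiguous and, read literally, yields no fluid-resolution rate by type; separately, the primary outcome and its analysis define fluid differently

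*Combined protocol and SAP*

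**What the plan says.** Part I (Aim and Hypotheses) sets out to evaluate eplerenone "in a controlled prospective fashion for both acute and chronic CSCR", and the hypothesis expects fluid to resolve in both. The inclusion criteria define the two types separately. The study schematic takes "20 patients with CSCR (Acute or Chronic" in any combination, with no number set for either type.

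On the primary analysis, Statistical Analysis says: "The primary outcome will be described by the proportion of patients without subretinal fluid on OCT at the end of the study period". It adds: "The 95% confidence interval (CI) for this proportion will also be estimated". No section plans this proportion by type.

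Among the Secondary (Exploratory) Outcomes, the one item that mentions type is "Proportion of acute vs. chronic CSCR patients". The rule that would apply to it is that "categorical secondary outcome measures will be described using frequencies and proportions".

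On what counts as fluid, the Primary Outcome section reads "Presence or absence of subretinal fluid and/or intraretinal fluid on OCT after 4 weeks of treatment", whereas the analysis sentence quoted above refers to subretinal fluid alone. The background notes that "Patients with chronic CSCR can also develop intra-retinal fluid in addition to sub-retinal fluid".

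**The concern.** A study that names two disease types in its aim would be expected to report its main result for each, at least descriptively. If the type item is followed as written, the report would say how many patients of each type enrolled and give one pooled resolution rate. A reader could not see what happened in acute or in chronic disease. Statistical Analysis says the data may be used to design later trials, and a trial in one type would need that type's rate. If the by-type summary is not written down in advance, its event, time point and fluid definition could be chosen after the results are known, in an unblinded study.

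The fluid definition is a separate defect and belongs to the pooled primary outcome. A patient whose only remaining fluid at week 4 is intraretinal is a failure under the Primary Outcome section and a success under Statistical Analysis. It matters here because a by-type rate would inherit the conflict, and the background describes intraretinal fluid in chronic disease.

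**Working it through.** **Inputs.** The planned total is 20 (Study Design). The interval method is exact, two-sided, 95% (Sample Size and Precision Calculations). The same section gives 10 patients at 70% success as its lead case. The documents fix no split by type, so the splits below are assumptions.

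**Formula.** For x successes in n, the Clopper-Pearson limits are lower = Beta quantile(0.025; x, n − x + 1) and upper = Beta quantile(0.975; x + 1, n − x).

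**The plan's own figure.** 7/10 gives 0.348 to 0.933, width 0.586, as stated. The other five rows of the table also reproduce to three decimals.

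**What the literal reading delivers.** With 10 acute patients among 20, the item reports 10/20 = 50% acute. That carries no information on resolution.

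**What the pooled rate can hide.** 14/20 gives 0.457 to 0.881 (width 0.424). With an assumed 10/10 split, 14 successes could be 7 + 7 or 10 + 4. The pooled line is identical in both cases. If the success rate is the same in both types, which is how the precision section treats it, the mix has no effect on the pooled rate.

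**What by-type reporting would deliver.**

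| Assumed group | Result | Exact 95% CI | Width |
|---|---|---|---|
| n = 10 | 4/10 | 0.122 to 0.738 | 0.616 |
| n = 10 | 7/10 | 0.348 to 0.933 | 0.586 |
| n = 10 | 10/10 | 0.692 to 1.000 | 0.308 |
| n = 15 | 12/15 | 0.519 to 0.957 | 0.438 |
| n = 5 | 4/5 | 0.284 to 0.995 | 0.711 |

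The intervals for 4/10 and 7/10 share the range 0.348 to 0.738. Even those for 4/10 and 10/10 overlap slightly (0.692 to 0.738).

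**Fluid definition.** Each patient with only intraretinal fluid left at week 4 changes the pooled rate by 1/20 = 5 points. Starting from an assumed 16/20 under the subretinal-only definition:

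- No such patient: 16/20, 0.563 to 0.943
- One such patient: 15/20, 0.509 to 0.913
- Two such patients: 14/20, 0.457 to 0.881

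In an assumed group of 10 chronic patients, each such patient is worth 1/10 = 10 points.

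**The case against.** The strongest reply is that the type item is a case-mix count. Such a count needs no event or time point, and the enrolled patients are its obvious denominator. If instead it was meant as resolution by type, the rule for categorical secondary outcomes already supplies counts and proportions. Only an interval is then missing, and a reader could calculate it. Both points stand. The fault is therefore ambiguity, and a reader who infers that the plan certainly reports nothing by type goes further than the text allows.

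It is also fair to say that this is a non-comparative, exploratory pilot with a stated reason for pooling: the precision section cites similar resolution rates after PDT and in a small chronic series on eplerenone. A reader might infer that the pooled primary proportion is invalid. The documents do not support that, since pooling follows from the plan's assumption and nothing planned is wrong because of it.

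The 10- and 15-patient rows of the precision table might be taken as intended group sizes by type. No text says so.

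On fluid, the background describes intraretinal fluid only alongside subretinal fluid, and entry requires subretinal fluid under the fovea. Isolated residual intraretinal fluid may be uncommon. That limits the likely size of the effect, but the two definitions still differ.

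**Conclusion.** The point holds as a gap between aim and planned reporting. Both types are named in the aim, one pooled rate is planned, and the only item on type gives the enrolment mix on its literal reading. Nothing else in the documents plans a resolution result by type. Adding one is a modest, cheap gain for later trial design.

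A reader might hope that by-type rates would show whether the types respond differently. At about 10 per type they seldom would, as the overlapping intervals show. No true by-type rate or mix is known from the documents, so the splits and counts used here only illustrate precision and masking. They do not estimate a bias.

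The conflict over what counts as fluid is real and stands apart from the type item. It is worth 5 points of the pooled rate per affected patient, and the documents do not say how many to expect.

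**What to change.** 1. Reconcile the fluid definition between Primary Outcome and Statistical Analysis, and use the single agreed definition for the pooled and by-type rates alike.
2. Reword the type item along these lines: *proportion without fluid on OCT at week 4, separately in acute and in chronic CSCR, with the number of each type and an exact 95% CI*. Report it descriptively beside the pooled figure, with no test between types.

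The cost is one reworded item, one agreed definition and two more lines in a results table. Type is already established at entry through the inclusion criteria, so no new data, visits or patients are needed. The drawback is wide intervals, and the text should say that the by-type rates are descriptive.

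By-type summaries of the continuous OCT changes are optional. Three measures at three visits for two types would add 3 × 3 × 2 = 18 summaries for the study eye alone.

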Eplerenone is a relatively safe medication, but it can lead to raised serum potassium levels (i.e., hyperkalemia), which can be potentially life-threatening. In a large clinical trial of patients with CHF, the incidence of serious hyperkalemia, defined as a serum potassium concentration ≥ 6 mEq/L, was 5.5% in the eplerenone group and 3.9% in the placebo group. Patients with a lower creatinine clearance at baseline had a higher incidence of serious hyperkalemia.[37]

Eplerenone comes in two doses, 25 mg and 50 mg. The standard dose for treatment of hypertension is 50 mg daily. For patients with an inadequate blood pressure response to 50 mg, the dosage is increased to 50 mg twice daily. For treatment of CHF, patients are started on 25 mg, and escalated to 50 mg within four weeks. Dose adjustment in CHF patients takes place based on serum potassium levels as follows: < 5.0 mEq/L – Increase to 50 mg once daily; 5.0 – 5.4 mEq/L – Maintain dose; 5.5 – 5.9 mEq/L – Decrease to 25 mg every other day; ≥ 6.0 mEq/L – Withhold and restart at 25 mg every other day when potassium levels fall to < 5.5 mEq/L.[38]

The other notable side effects with aldosterone-receptor antagonist medications are related to cross-reactivity with sex hormone receptors. Eplerenone has a much lower incidence of anti-sex hormone effects than spironolactone. With eplerenone, sex hormone-related events, such as breast enlargement in men, breast pain, or menstrual abnormalities, have been reported in up to 2.5% of patients, although some studies reported no such events.[39-41]

Because of the elevations in serum potassium concentrations and consequent increased risk for hyperkalemia with eplerenone, use of this drug is contraindicated in patients at increased risk for hyperkalemia, including those with a serum potassium concentration > 5.5 mEq/L, type 2 diabetes and microalbuminuria, a serum creatinine concentration > 2 mg/dL in men and > 1.8 mg/dL in women, or a creatinine clearance < 50 mL/min, and during concomitant administration of potassium supplements, potassium-sparing diuretics, and/or potent CYP3A4 inhibitors.[38] It is recommended to check serum potassium and creatinine before initiating eplerenone therapy, followed by serum potassium within the first week and at one month after the start of treatment.[38]

Part II

Experimental Protocol:

Study Design

[figure not shown]
- Prospective, consecutive, non-randomized, non-blinded, non-comparative interventional pilot study

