5. *Fluorescein Angiography*: Fluorescein angiography will be acquired at diagnosis and at 4 weeks after treatment initiation. Angiography will be explained to patients by either the physician or the ophthalmic nurse administering the intravenous dye. Patients routinely give verbal consent stating they understand the procedure and potential risks of fluorescein angiography. The procedure involved a special water-soluble dye (fluorescein) that is injected intravenously. As the dye passes through the blood vessels of the choroid and retina, the photographer takes a series of photographs in rapid succession, over a period of 5-10 minutes. The possible side effects of fluorescein angiography are discussed below.

Laboratory Testing: After initial screening, serum potassium and creatinine will be evaluated at 1 and 4 weeks after baseline. *See below for dosing adjustment instructions based on potassium levels.* Additional serum tests of electrolytes, liver function tests, uric acid, and a fasting cholesterol panel will be obtained before treatment and 4 weeks after baseline

Baseline and 4-week visits: Serum potassium, sodium, BUN, creatinine, glucose, chloride, total CO₂, calcium, AST, ALT, GGT, alkaline phosphatase, total and direct bilirubin, uric acid, albumin, total protein, fasting total cholesterol, fasting LDL, fasting LDL, fasting triglycerides. The initial and final blood draws will be roughly 7.5 to 10 ml of blood, or 2 teaspoons.

6. **1-week visit:** Serum potassium and serum creatinine. The 1-week blood draws will be roughly 4 ml of blood, or 1 teaspoon.

7. **Blood pressure:** Systolic and diastolic blood pressure will be recorded at all visits. Blood pressure will be measured in the seated position. When blood pressure is scheduled at the same time point as a blood sample draw, the blood pressure will be measured first.

8. The subject's participation in the research may be terminated by the principal investigator or co-investigator if there is any type of medical emergency or urgency that needs to be attended to first. If a subject decides to withdraw from the research, the patient will be offered routine ophthalmologic care at NEEC. If the patient prefers, he or she can be referred to an outside ophthalmologist for continued eye care. The subject's data and collected blood and urine samples will be discarded, although the reason for screen failure will be noted after the patient demographic data is de-identified.

Eligibility

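### Week-1 creatinine is measured, but the dose and stopping rules give no action if it crosses a renal limit that the protocol itself calls a contraindication

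*Combined protocol and SAP*

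**What the plan says.** The dosing instruction is in Part II, Study Design: "Treatment will be the standard dose of eplerenone, 50 mg pills taken one pill daily over four weeks". The same list schedules the first on-treatment blood test: "Serum potassium and creatinine levels will be re-tested at the 1 week visit". Both tests are repeated at week 4 with the full panel. The Laboratory Testing text under Study Visits refers forward to the dosing rules with the words "See below for dosing adjustment instructions based on potassium levels".

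Those rules are in the section Dose adjustment and/or stopping criteria, whose only sub-heading is Serum potassium criteria. For a week-1 potassium from 5.0 to below 5.5 mEq/L, "dosing will be decreased to 25 mg every day and serum potassium will be rechecked at 1 week". If potassium stays in that range, the dose falls to 25 mg on alternate days and then to nothing. For higher values, "If serum potassium is ≥ 5.5 mEq/L at 1 week, eplerenone will be withheld". No other laboratory value appears in the section.

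The Background section Eplerenone for CSCR says that "use of this drug is contraindicated in patients at increased risk for hyperkalemia". It counts among them anyone with creatinine above 2 mg/dL (men) or 1.8 mg/dL (women), or clearance below 50 mL/min. The same renal limits appear in Initial Diagnosis and Enrollment, item 4, and in Exclusion Criteria, item 5, both times as checks made at screening.

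One other written stopping route exists. Study Visits, item 8, lets the investigator end a subject's participation when an emergency or urgent medical need has to come first.

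**The concern.** The protocol collects a week-1 creatinine without saying what to do with it. This is the only scheduled creatinine that could change dosing, because the week-4 sample is taken as the 28-tablet course ends. Clearance is not scheduled to be derived at week 1 at all.

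The protocol gives its own reason why this matters. It describes hyperkalemia as potentially life-threatening, and it reports from a heart-failure trial that "Patients with a lower creatinine clearance at baseline had a higher incidence of serious hyperkalemia". A potassium below 5.0 mEq/L at week 1 is reassuring on that day, but it does not show how potassium will behave over the next three weeks if renal function has fallen. Without a rule, two patients with the same week-1 result could be handled differently, and following the written schedule would keep a patient on a drug that the protocol says is contraindicated.

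**Working it through.** The plan has no figure of its own on this point. Its only design calculation, the exact confidence-interval table, reproduces (for 10 patients and a proportion of 0.70: 0.348 to 0.933, width 0.586) and plays no part here. The check is a comparison of sections plus calendar arithmetic.

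**Where each limit is used**

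| Limit | Contraindication (Background) | Entry limit (exclusion 5) | Action on treatment |
|---|---|---|---|
| Potassium | > 5.5 mEq/L | excluded at ≥ 5.0 | step-down from 5.0; withheld at ≥ 5.5 |
| Creatinine, men | > 2 mg/dL | excluded at > 2 | none stated |
| Creatinine, women | > 1.8 mg/dL | excluded at > 1.8 | none stated |
| Clearance | < 50 mL/min | excluded at < 50 | none stated; not scheduled to be derived |

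For potassium, entry is set 5.5 − 5.0 = 0.5 mEq/L inside the contraindication, and treatment rules follow. For renal function, the entry limits equal the contraindication limits. A patient may therefore enter with a clearance of exactly 50 mL/min, and any fall crosses the limit.

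**Calendar for a patient who crosses a renal limit at week 1 with potassium < 5.0 mEq/L**

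Inputs: 28 tablets of 50 mg, one daily (Study Visits, item 1); visits at days 0, 7, 14 and 28; scheduled on-treatment potassium and creatinine at days 7 and 28 (Laboratory Testing).

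- Time to the next scheduled potassium: 28 − 7 = 21 days.
- Doses left: 28 − 7 = 21, and 21/28 = 75% of the course.
- Drug left: 21 × 50 = 1,050 mg of 28 × 50 = 1,400 mg.
- Doses left when the week-4 creatinine is drawn: 28 − 28 = 0.

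For reference, when week-1 potassium is 5.0 to below 5.5 mEq/L, the plan halves the dose (25/50) and rechecks after 7 days, a third of the 21-day gap (7/21). The two patients differ in potassium, so some difference in handling is expected. The comparison shows only that a one-week recheck is already part of this plan.

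**Other text that might supply an action**

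- The adverse-event definitions count laboratory changes that the investigator judges clinically significant. Recording of AEs and SAEs requires review and a causality assessment. Neither sets a dose change.
- Study Visits, item 8, is discretionary and names no creatinine or clearance value.

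No section gives a hold, reduction or stop for an on-treatment renal result.

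**The case against.** The strongest reply is that the protocol already meets the monitoring advice it cites. That advice asks for potassium in the first week and at one month, and the cited heart-failure titration is potassium-only too: "Dose adjustment in CHF patients takes place based on serum potassium levels as follows". The protocol is stricter than that scheme, reducing the dose at 5.0 to below 5.5 mEq/L where the scheme maintains it at 5.0 to 5.4, and withholding at 5.5 rather than 6.0. It adds creatinine at weeks 1 and 4. The renal limits are markers of hyperkalemia risk, and potassium is measured in the same week-1 sample. The evidence on clearance concerns baseline values in another population. All of this stands, and it keeps the point modest. It does not say what to do with a result that the protocol chose to collect and whose limits it calls contraindications.

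A second reply is clinical judgement: a physician who sees such a creatinine would probably act, and item 8 gives written authority to end participation. That also stands. However, a symptomless creatinine rise need not count as an emergency or urgent matter, and ending participation is not the same as holding drug while keeping the patient in follow-up.

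Stronger readings are tempting, and the documents do not support them:

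- A reader might infer that potassium is the only route to stopping. Item 8 shows otherwise; the potassium-only description fits the prespecified numeric rules.
- A reader might infer that the protocol orders continued dosing after a renal limit is crossed. It is silent, and 50 mg daily is what remains by default.
- A reader might infer an equal gap for interacting drugs started on treatment. The drug clause in exclusion 5 can fairly be read as a prohibition for as long as eplerenone is taken, and patients are asked about new medicines (Method of detecting AEs and SAEs). Only the action is unnamed.

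**Conclusion.** The point holds as an omission, not a contradiction. The numeric dose and stopping rules do not cover an on-treatment renal result, although the test is scheduled and the limits are already written down.

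Its size is a ceiling: up to 21 of 28 doses, and 21 days to the next scheduled potassium. This assumes that a renal limit is crossed at week 1, that potassium is then below 5.0 mEq/L, and that nobody acts on the result, including at the week-2 visit. It is not an estimate of expected exposure.

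The documents give no frequency for this state. With at most 20 participants, screening of potassium and creatinine within the week before treatment, and investigator discretion, it should be rare. A reader might take the 5.5% versus 3.9% serious hyperkalemia in the heart-failure trial as the rate at stake; it comes from a different population and does not measure this event. Sample size, precision and the primary analysis are unaffected. This is a cheap improvement in patient safety that the sponsor should make.

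**What to change.** Add a renal paragraph to Dose adjustment and/or stopping criteria:

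1. Derive clearance from the week-1 creatinine with the same formula as at screening, and name that formula. Item 4 of Initial Diagnosis and Enrollment and exclusion 5 give the limit but no formula.
2. If a renal limit in exclusion 5 is met (creatinine > 2 mg/dL in men or > 1.8 mg/dL in women, or clearance < 50 mL/min), withhold eplerenone and repeat potassium and creatinine no later than the existing week-2 visit.
3. Resume only if both are back within the exclusion 5 entry limits: potassium < 5.0 mEq/L, and creatinine and clearance no longer meeting an exclusion. Otherwise the drug stays off.
4. The patient stays in follow-up through the week-4 OCT in either case.

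As a secondary clarification, state that the drugs listed in exclusion 5 are prohibited throughout treatment and that eplerenone is withheld while one is taken.

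Cost: a short amendment, one clearance calculation per patient, an occasional extra draw of about 4 ml (the volume the protocol gives for the same two tests at week 1), and a few interrupted courses. The potassium rules already allow such interruptions.
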